5.5.5 Stopping Rules

The study medication administration and the light delivery are planned to last no longer than approximately 32 minutes. This time will be precisely monitored. The drug or light administration can be discontinued at any time by the investigator in case of a significant adverse event (AE).

Because this study consists of a single administration of the study medication and a single session of light delivery, there is no need to establish rules for stopping the study treatment during the follow-up period.

The Sponsor may terminate the study at any time in a center:

1. If the investigator is non-compliant with the protocol, the regulatory requirements or the ICH-GCP;
2. If the CRF completion or drug accountability is inadequate, and the investigator is unable to take corrective action in any of these cases;
3. In case of failure to recruit subjects.

The entire study may be terminated for medical reasons. In addition the Sponsor retains the right to end the study at any time if the study cannot be carried out as agreed upon in the study protocol. In case of premature termination the Investigators, IRB/IECs and regulatory authorities will be informed by the Sponsor.

The Sponsor also reserves the right to terminate the study at any time for administrative reasons. The Sponsor will not reimburse the Investigator for the evaluation of subjects if the evaluations are conducted in a manner other than that specified in this protocol.

5.5.6 Replacement of premature withdrawals from trial

The Sponsor reserves the right to replace a subject who is removed or withdraws from the study before the month 3 biopsy with a new subject. A subject who is removed or withdraws after the month 3 biopsy will not be replaced.

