This study is a phase IIb trial using optimal dose of TOOKAD® Soluble and optimal light-energy level conditions that were determined in previous phase I and II studies and confirmed by the phase III studies among patients with localized prostate cancer. Partial gland ablation therapy using thermal approaches, as an alternative to radical treatments for low-volume prostate cancer, is a treatment option currently being offered to men with prostate cancer in the U.S. as a tailored means to manage their disease with fewer side effects. Previous studies of TOOKAD® Soluble treatment have suggested that this non-thermal approach is an effective therapeutic strategy to achieve ablation of the prostatic tissue that contains the cancer lesion in this patient population. Considering the available clinical data, a phase IIb is considered appropriate at this stage, with the main aim of confirming, in intermediate risk patients, previous findings in low and favorable intermediate risk prostate cancer patients. Moreover, a single center design was also considered appropriate, as it allows for optimal standardization of the technique and better control over data acquisition.

NUMBER OF PATIENTS:

In order to obtain at least 44 evaluable patients, a total of 50 patients will be included and will be treated with TOOKAD® Soluble VTP in this study.

DRUG DESCRIPTION AND PREPARATION:

TOOKAD® Soluble - padeliporfin di-potassium (WST11) Drug Product is a dark coloured powder for solution for injection. It is packaged in amber glass vials. It is manufactured in two different presentations:

- 200 mg TOOKAD® Soluble in a 30 mL vial with blue flip-off cap, to be reconstituted, just before administration, with 20 mL of 5% dextrose solution for injection
- 400 mg TOOKAD® Soluble in a 50 mL vial with white flip-off cap, to be reconstituted, just before administration, with 40 mL of 5% dextrose solution for injection

The two presentations have the same formulation which is produced in exactly the same process and they differ only in the amount of TOOKAD® Soluble per vial, the size of the vial and the colour of the flip-off cap.

For both presentations the final concentration of TOOKAD® Soluble solution to be injected is 10 mg/mL.

INCLUSION CRITERIA:

Subjects will be eligible for inclusion in the study if all of the following criteria are met:

1. Men over 18 years of age.

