4 TRIAL DESIGN

4.1 Overall study design and plan

This is a single center, single-arm, open-label, 60-month follow-up phase IIb clinical trial. Men with localized prostate cancer will receive TOOKAD® Soluble -VTP treatment under general anesthesia. Prior to the TOOKAD® Soluble- VTP treatment, patients will undergo routine ultrasound examination in the operating room for morphometric description of the prostate and to facilitate accurate treatment guidance for the treatment with TOOKAD® Soluble- VTP. Treatment will then be applied to the prostate gland as a focal therapy, hemiablation procedure designed to destroy the lobe of the prostate gland that contains the Gleason score 7 (3+4) cancer. Afterwards, patients will be followed for 12 months with clinical evaluation, questionnaires on QOL, erectile and urinary functions, and PSA testing. In addition, treatment outcomes will be assessed based on prostate biopsy results at 3, 12, 24, 36, 48 and 60 months after the TOOKAD® Soluble treatment. All patients will undergo biopsy at 3 and 12 months after the TOOKAD® treatment. Thereafter, biopsy will be performed for cause per institutional standards. If the Month 3 biopsy is positive for any cancer patients will be allowed a single re-treatment by TOOKAD® Soluble VTP. However, patients with evidence of clinical deterioration on the same side such as worsening Gleason score, increased core involvement with cancer tumor grades on the 3-month biopsy and/or rising PSA will be withdrawn from the study and proceed with standard care. In addition, patients who experience treatment-related Grade 3-4 adverse events during their first treatment will not be re-treated at month 3, will be withdrawn and proceed with standard care if the month-3 biopsy contains cancer on the same or contralateral side, unless justification for continuing on study is specifically sought and approved from the IRB.

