5.5.4 Subject withdrawal

The criteria for terminating participation in the study are detailed below:

1. Serious adverse event that is study-related (see definition further below), as recommended by the Investigator, patients with grade 3 or 4 adverse events following their initial treatment who have evidence of treatable prostate cancer on month 3 biopsy will not undergo re-treatment, will be withdrawn from the study and proceed with standard of care unless justification for continuing on study is specifically sought and approved from the IRB.
2. Subject withdrawal: at any time, a subject can withdraw from the study at his request or on the basis of the Investigator's clinical judgment.
3. Patients with evidence of clinical deterioration on the same side such as Gleason grade 5 cancer, more than 2 sextants including Gleason grade 4 cancer on the treated side on the 3-month re-biopsy will be withdrawn from the study and proceed with standard care.
4. Major protocol violation, defined as any violation that may impact the safety of a study subject.
5. Termination of the study by the Sponsor.

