10.2.2.5 Drop-outs and censored patients

All subjects who withdraw from the trial before the VTP procedure will be considered as drop-outs. Every effort will be made to minimize dropouts.

Eligible subjects who undergo additional radical therapy (surgery or radiation) after the VTP procedure or receive medical therapies (hormone or chemotherapies) will be kept in the intention to treat population but will be excluded from the per protocol population.

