**IPSS questionnaire**

Scores with at least 1 but not more than 50% missing items will be imputed using the formula:  $S = s \times T \div t$  where s is the observed score, S is the imputed score, T is the maximum total score for the IPSS and t is the maximum score possible from the completed questions. Missing total scores will be imputed using a multiple imputation method (Markov Chain Monte Carlo method).

Other missing data, including biopsy data, will not be replaced.

A subject with missing Month 12 biopsy will be counted as failure for the primary analysis.

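### A treated man who leaves before the Month 3 biopsy may be replaced at the sponsor's option, and the SAP's efficacy population lets him drop out of the primary denominator

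*Protocol*

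**What the plan says.** Protocol 5.5.6 gives the sponsor an option: "The Sponsor reserves the right to replace a subject who is removed or withdraws from the study before the month 3 biopsy with a new" [participant]. It then sets the limit: "A subject who is removed or withdraws after the month 3 biopsy will not be replaced". It gives no criterion for using the option, no cap, no independent decision and no reporting requirement.

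Protocol 10.2.2.5 has a separate category for men who leave before treatment: "All subjects who withdraw from the trial before the VTP procedure will be considered as drop-outs". Section 5.5.6 is not tied to it.

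On leaving the study, protocol 5.5.4 says "a subject can withdraw from the study at his request or on the basis of the Investigator's clinical judgment". Section 5.5.3 is narrower: the investigator may withdraw a man only where continuing would endanger his health or welfare.

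On design, protocol 4.1 states: "This is a single center, single-arm, open-label, 60-month follow-up phase IIb clinical trial". On numbers, the synopsis states: "In order to obtain at least 44 evaluable patients, a total of 50 patients will be included and will be treated".

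The SAP defines the efficacy population as men who, among other conditions, complied with follow-up and have 12-month biopsy data, and it uses that population for all efficacy analyses. Its missing-data section says: "A subject with missing Month 12 biopsy will be counted as failure for the primary analysis". Neither document says how a replaced man is counted.

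**The concern.** In a single-arm trial compared with a fixed 70%, the protection against selection is that every treated man is counted. Here the time limit for replacement falls after treatment. By then the open-label team knows adverse events and the Month 1 PSA. It may also know the Month 3 PSA and MRI, since protocol 7.1 and 8.2 use MRI lesions to target biopsies.

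If men who are doing badly are more likely to leave in this window, and are then both absent from the analysis and replaced by men with a fresh chance of response, the observed rate overstates the rate among all treated men. At stake is the chance of declaring success when the true rate is only 70%.

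**Working it through.** **1. Does the option reach treated men?** Yes. VTP is Visit 2 (protocol 6.4.2) and the Month 3 biopsy is Visit 5 (6.4.5). A man who leaves between them has been treated and may be replaced.

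**2. What happens to him in the analysis?**

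| Text | Effect on a treated man who leaves before Month 3 |
|---|---|
| Protocol 5.5.6 | May be replaced; silent on how he is counted |
| SAP, Efficacy population | No 12-month biopsy, so he is out |
| SAP, missing-data rule | No Month 12 biopsy, so he is a failure |
| SAP, Primary efficacy analysis | Counts as failures men with pattern 4 or 5 found before 12 months who then receive radical therapy; does not reach a man who left before any post-treatment biopsy |
| Protocol 10.2.2.4 (ITT) | Kept, but the set is named only for descriptive statistics |
| SAP, Safety population | Kept, for safety only |

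The second and third rows conflict. In a set limited to men with a 12-month biopsy, the missing-equals-failure rule has nobody to act on. So the efficacy population definition is what removes him; 5.5.6 then allows his place to be refilled.

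**3. Reproducing the plan's figure.** Inputs from the SAP: null 70%, assumed rate 83.6%, one-sided alpha 10%, power 80%. With z = 1.2816 and 0.8416, the normal approximation is

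N = [(1.2816·√(0.70·0.30) + 0.8416·√(0.836·0.164)) / 0.136]² = 43.7, so 44, as stated.

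For the rule of at least 35 of 44, exact binomial tails give P(X ≥ 35 | 0.70) = 10.9% and P(X ≥ 35 | 0.836) = 82.6%. The one-sided 90% Clopper-Pearson lower bound for 35/44 is 69.6%, which meets the criterion only after rounding to 0.70. The SAP does not name the interval method; exact is assumed here. The protocol states 5% rather than 10%, which is a separate matter; the SAP rule is used because it gives the pass mark.

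**4. Dropping men selectively.** Assume a true rate of 70% among all treated men. A fraction f of would-be failures leaves early and is not analysed, no would-be responder leaves, and 44 men are analysed.

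- Rate among those analysed: 0.70 / [0.70 + 0.30(1 − f)]
- False success: P(X ≥ 35 | n = 44, that rate)
- Mean number treated to reach 44 analysed: 44 / (1 − 0.30f)

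| f (assumed) | Rate analysed | False success | Mean treated |
|---|---|---|---|
| 0 | 70.0% | 10.9% | 44.0 |
| 10% | 72.2% | 17.9% | 45.4 |
| 20% | 74.5% | 28.1% | 46.8 |
| 30% | 76.9% | 42.0% | 48.4 |

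The last column matters: on average every row fits within the 50 men already planned. The inflation therefore needs only that the men be dropped from the analysis, and can arise with no replacement. If responders and failures leave at the same rate, the analysed rate stays 70% and false success stays 10.9%.

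**5. How thin the margin is.** If one treated man is swapped out and 35 of the analysed 44 respond, the trial passes. Counting him as a failure gives 35/45 = 77.8%, lower bound 67.8%, which does not pass. With three such men, 35/47 has a lower bound of 64.5%.

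**6. If all treated men are analysed.** Under the SAP rounding with exact bounds, the pass mark is 36/45, 37/46, 38/47, 38/48, 39/49 or 40/50. For 40/50, exact alpha is 7.9% and power 81.3% at 83.6%.

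**The case against.** The strongest reply is that 5.5.6 does no harm by itself. Nothing in it deletes a replaced man from the analysis, and the missing-data rule makes no exception for him. If that rule governs every treated man, replacement adds a man without removing one and the bias goes. This stands, and it is why the point rests on 5.5.6 together with the efficacy population. It does not dispose of the point, because the SAP as written supports both readings.

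A reader might infer that men who fail early can simply be exchanged for new ones. The documents do not support that. The primary endpoint is histology at Month 12, no post-treatment biopsy is scheduled before the cut-off, and the second sentence of 5.5.6 bars replacement afterwards. What can be known is adverse events, PSA and possibly MRI. The sponsor decides on replacement, but leaving rests with the man or the investigator, on grounds that 5.5.3 and 5.5.4 state differently and that must be reconciled.

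A reader might also take 17.9% or 28.1% as the effect of the replacement clause, or as an estimate. They are neither: step 4 shows that they need no replacement, and the documents give no value for f. The nearest evidence is in protocol 2.2.4, where two Gleason 3+4 men in the earlier trial had no biopsy because of adverse events (stroke and perineal pain), neither of them an oncological signal. Their result is given as 8/8; with both counted as failures it is 8/10. Such losses occur and can move a rate, but this does not show that they follow prognosis.

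Finally, the six places between 44 and 50 may be meant for losses after Month 3, so the allowance does not prove that replacing treated men is unnecessary.

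**Conclusion.** The concern holds in this form. The plan lets a treated man who leaves before the Month 3 biopsy be replaced at the sponsor's option, and its two rules on a missing Month 12 biopsy disagree on whether he stays in the primary denominator. If he is dropped and leaving is related to outcome, the response rate and the false-success risk rise: from 10.9% to 17.9% or 28.1% if 10% or 20% of would-be failures are dropped. This assumes a true rate of 70%, the 35/44 rule and no loss of would-be responders. The fractions are illustrative, and the effect is nil if leaving is unrelated to outcome. No misuse is implied. It should be corrected, because the margin at the pass mark is a single man.

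**What to change.** 1. In protocol 5.5.6, limit replacement to men who leave before the VTP procedure starts, with start defined as in the SAP safety population (which includes the start of anaesthesia).
2. In the SAP, remove the requirement for 12-month biopsy data from the primary analysis set, and make sure that the follow-up compliance condition cannot exclude the same men. Every man in whom VTP was started, including any already replaced, stays in the primary denominator, with a missing Month 12 biopsy counted as failure. The present efficacy population can remain as a supportive analysis.
3. Restate the success rule for the number actually analysed, name the interval method, and tabulate the pass marks (for example 40/50).
4. List any replaced men with the time and reason.

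The first item alone would not close the gap, because the efficacy population could still drop the man.

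The cost is an amendment to both documents and a reported rate that may be lower. There is also a power cost to face openly. The 81.3% for 40/50 needs 83.6% to hold with missing counted as failure, yet protocol 10.1 derives 83.6% from men who had biopsies. If 83.6% applies only to men with a biopsy, power is P(X ≥ 40 | n = 50 − m, 0.836) when m of 50 lack one: 72.4% for m = 1, 48.5% for m = 3 and 13.1% for m = 6. No extra men are needed if nearly all have the biopsy; otherwise the sample size should be revisited.

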6 TREATMENT OF SUBJECTS

6.1 Entry into study

6.1.1 Entry Biopsy

Only patients with at least one prior prostate biopsy will be considered. Additionally:

- The biopsy must demonstrate any Gleason score 7 (3+4) prostate adenocarcinoma in 1 or 2 sextants on one side of the prostate gland.
- The biopsy must include a minimum of 12 cores and must have at least 1 core from each prostate sextant.
- All cores from the prior biopsy must have been evaluated and results confirmed at the treating institution.
- Standard definition for prostate sextant anatomy will be used: Right and Left; Apex, Mid and Base. Transition zone biopsies, if present, will be considered as Mid gland.
- Targeted biopsy of suspicious lesions seen on MRI that meet PIRADS (version 2) criteria for level 4 or 5 lesions will be required before patients may be considered eligible.
- Patients who meet initial biopsy eligibility criteria with PIRADS (version 2) criteria lesions of level 3 or less will not require targeted biopsy.
- If a patient has undergone biopsy without MRI and subsequently undergoes MRI but no suspicious (PIRADS 4 or 5) lesions are observed, additional biopsy is not needed for inclusion.

6.1.2 Consent to participate

Patients will be enrolled if they have given written consent to participate. They will be informed of the local and international recommendations for the treatment of their condition (localized prostate cancer) and the nature of the available interventions.

6.1.3 Assignment of Subject Identification

A subject identification number will be assigned in the CRF at Screening. This identification number should be used in every study-related documents. To maintain confidentiality, the subject's name should not be

recorded on any study document other than the informed consent form. This identification number differs from the treatment number(s) that will be assigned and reported in the CRF on the day of the VTP procedure.

6.2 Treatment Guidance (TG)

6.2.1 Aim of Treatment Guidance

The aim of the treatment guidance is to determine the optimal light dose by estimating the number of fibers and for each fiber its position regarding the external template and the length of its diffusing tip.

This fibers configuration defines the treatment effect boundaries (in 3 dimensions).

6.2.2 TOOGUIDE TRUS Treatment Guidance software

The Treatment Guidance is done with the aid of the Treatment Guidance Software TOOGUIDE TRUS (see Appendix 6). The procedure is performed or supervised by the urologist in charge with the treatment.

TOOGUIDE TRUS allows acquiring TRUS images of the patient while he is in the treatment position, to define the prostate contours, the target and the optimal fibers configuration to maximize light dose in the target while sparing the surrounded tissues.

6.2.3 Treatment Conditions

Treatment guidance will help to determine the number and position of laser fibers to be inserted, with the length of illumination necessary to achieve a Light Density Index ≥ 1 in the targeted tissue. In case of unilateral disease, focal treatment of one lobe will be applied. In case of bilateral disease (discovered at entry or during follow-up), bilateral treatment will be applied consecutively or simultaneously. Retreatment of lobes found positive for cancer at 3-months follow-up will be allowed, provided there is no sign of cancer progression in the treated lobe and the patient did not experience grade 3 or 4 adverse events.

6.2.4 Definition of the Light Density Index (LDI)

The Light Density Index (LDI) is defined, for each zone to be treated, as the ratio of the cumulative length of illumination tip of the fibers (in cm) per cubic centimeter of the targeted zone. It is calculated as:

$$\text{LDI} = \text{Total length of illumination tips of the fibers (in cm)} / \text{Treatment volume (in cc)}$$

Where:

1. The total length of illumination tip of the fibers is the sum (in centimeters) of the length of each illumination tip of the fibers used during the procedure for the treated lobe.
2. The treatment volume (in cc) is calculated by the TOOGUIDE- TRUS software after delineation of the prostate by the investigator on the TRUS image.

3. An LDI equal or superior to 1.0 should be achieved for each zone to be treated.

6.2.5 Choice of zones to be treated

The treatment guidance will be conducted in order to treat the lobe of the prostate that contains cancer lesions. Prior biopsy data will be used to determine the lobe to be treated (target treated zone).

Treatment guidance will use the enrollment biopsy results and TOOGUIDE- TRUS software.

The plan will indicate the zones to be treated.

In case of unilateral disease, focal treatment of one lobe will be applied. In case of bilateral disease (discovered at entry or during follow-up), bilateral treatment will be applied consecutively or simultaneously.

6.2.6 Approaches for Protection of adjacent tissues in Treatment Guidance

To ensure that the rectum and urinary sphincter will not receive excessive light doses, a safety margin of at least 5mm will be maintained between the light delivery fibers and:

1. the rectal wall,
2. the apex of the prostate,
3. the urethra.

6.3 TOOKAD® Soluble VTP treatment procedure

6.3.1 Overview of procedure

The VTP procedure²⁶ will consist of a single, 10 minute infusion of 4mg/kg TOOKAD® Soluble. The drug will be activated by laser light at 753nm, with a dose of 200J/cm, and a fixed power of 150mW/cm, given over 22min 15s and delivered using interstitial optical fibers, inserted using a transperineal route, into the prostate gland:

1. A transperineal template is used for the placement of the transparent catheters which are positioned in the prostate under transrectal ultrasound image guidance.
2. The optical fibers are then inserted into the catheters.
3. The drug infusion begins once the catheter positioning is finalized.
4. The light delivery begins immediately after the completion of the drug infusion.

6.3.2 Study medicine TOOKAD® Soluble

TOOKAD® Soluble is a powder for solution for injection, presented in 200 mg or 400 mg vials. Before administration, the product is extemporarily reconstituted with a 5% solution of Dextrose, to reach the final concentration of 10 mg/mL and the solution is kept protected from light.

After preparation of the drug, the syringes, the infusion lines and the point of injection will be protected from light until the end of the injection.

Subjects are required to fast per institutional standards before the VTP procedure.

The duration of injection will be the same for all the subjects (10 minutes). A single dose of 4 mg/kg of TOOKAD® Soluble will be administered.

